| ICF | Informed Consent Form |
| IFU | Instructions for Use |
| IRB | Institutional Review Board |
| PHI | Protect Health Information |
| PI | Principal Investigator |
| QoL | Quality of Life |
| SAE | Serious Adverse Event |
| UPHS | University of Pennsylvania Health System |

CONFIDENTIAL

This material is the property of the University of Pennsylvania.

Study Summary

| | |
|--|--|
| Title | Prospective evaluation of minimally invasive facial cosmetic procedures through measured volumetric changes and patient reported outcomes |
| Short Title | Galderma - Prospective |
| IRB Number | 827003 |
| Protocol Number | NCT 03460158 |
| Phase | Post-market Study |
| Methodology | Prospective comparison of the dermal fillers for the treatment of age related aesthetic changes. |
| Study Duration | The active portion of the study will be the baseline visit and observational follow-up will occur approximately at baseline visit, 14 days, 28 days, and 90 days for a total of 90 day of patient participation. |
| Study Center(s) | University of Pennsylvania Health System (Penn Medicine) |
| Objectives | 
Primary:
 
Determine patient satisfaction with minimally invasive volume correction using patient reported outcomes and satisfaction with the validated survey FACE-QDetermine the volumetric changes over 90 days 
Secondary:
 
Correlate degree of patient satisfaction with 3-dimensinal image analysis. |
| Number of Subjects | 100 subjects |
| Main Inclusion and Exclusion Criteria | 
Inclusion Criteria
 
Female patientsBetween the age of 40 - 65 
Exclusion Criteria
 
Male patientsPrior surgical facial rejuvenation proceduresPrior minimally invasive rejuvenation procedure ≤ 12 monthsKnown contraindications to devices or drugs used in this studyFacial paralysisCongenital facial asymmetryPregnant womenPatient actively taking blood thinners |

| | |
|--|---|
| Investigational Product (drug, biologic, device, etc.) | Restylane-L® used in the nasolabial folds and marionette lines up to a total of 4cc injections |
| For Device include the planned use | Restylane-L® Lyft used in the nasolabial folds and marionette lines up to a total of 2 cc injections |
| For Drug, food, cosmetic, etc. include the dose, route of administration and dose regimen | Up to 1cc injections of Restylane® Silk may be placed in the lips and cutaneous vermillion (up to 2 cc total) Up to a total of 4cc injections of Restylane-L® Lyft may be placed in the malar region |
| Duration of administration | Injections to be placed during clinic visit. |
| Reference therapy | None |
| Statistical Methodology | Standard descriptive statistics will be used to summarize baseline characteristics and study outcome measures at each visit, both overall, and within each arm. The validated FACE-Q will be used to determine patient satisfaction for each arm. Mean and standard deviation calculation with regression analysis will be performed for all survey variables. Analysis of variance will also be performed. The baseline and post treatment measurements from the Vectra 3D images will determine volumetric changes of the injections over time. The average volume change will be calculated. A correlation between patient satisfaction and volumetric changes will be calculated. |

Prospective evaluation of minimally invasive facial cosmetic procedures through measured volumetric changes and patient reported outcomes

This study will be conducted in full accordance with all applicable University of Pennsylvania Research Policies and Procedures and all applicable Federal and state laws and regulations including [as applicable include the following regulations as they apply 45 CFR 46, 21 CFR Parts 50, 54, 56, 312, 314 and 812 and Good Clinical Practice: Consolidated Guidelines approved by the International Conference on Harmonisation (ICH). Note: Only include ICH compliance if the study will actually comply with these requirements.] All episodes of noncompliance will be documented.

1 Introduction

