2.1 Primary Objective

- To determine and compare patient reported outcomes and satisfaction with the validated survey FACE-Q over 90 days.
- To determine and compare the volumetric changes over 90 days

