4.5 Total Number of Subjects and Sites

Total accrual will be 100 patients. The aim will be to enroll all subjects at the University of Pennsylvania Health System (UPHS).

5 Study Intervention

The initial consultation by the principal investigator will determine the injection area and the volume of the injections. Injections of the fillers will be used according to the FDA approval indicated use. All three areas will be injected (nasolabial folds, marionette lines, and lips).

Restylane-L® used for the nasolabial folds and/or marionette lines up to a total of 4 cc (2 cc/side).
Restylane-L® Lyft used for severe nasolabial folds and or marionette lines up to a total of 2 cc (1 cc/side)
Restylane-L® Lyft used for malar deflation will receive up to a total of 4 cc of (2 cc/side)
Restylane® Silk in the lips and cutaneous vermillion used for perioral volume loss will receive up to 1cc per lip.

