8.4 Statistical Methods

8.4.1 Baseline Data

Standard descriptive statistics will be used to summarize baseline characteristics and study outcome measures at each visit, both overall, and within each arm.

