8.4.2 Efficacy Analysis

The validated FACE-Q will be used to determine patient satisfaction for each arm. The Mirror Software 3D software (Canfield Scientific Inc, Fairfield, New Jersey) will calculate the volumetric changes by comparing the treated area after filler injection to the baseline images. The baseline and post treatment measurements from the Vectra 3D images will determine volumetric changes of the injections over time. All volumetric measurements will be recorded in milliliters, and the average volume change will be calculated. A correlation between patient satisfaction and volumetric changes will be calculated.

CONFIDENTIAL

This material is the property of the University of Pennsylvania.

Statistical tests will be performed as determined by the study team. Mean and standard deviation calculation with regression analysis will be performed for all survey variables. Analysis of variance will also be performed.

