11.2 Benefits

Subjects participating in this trial will not directly benefit participating in this study. If assigned to the treatment group, the patient will receive the treatment described in the initial consultation. If assigned to the control group, they may not receive the desired benefits of the requested consultation.

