11.3 Risk Benefit Assessment

Subjects participating in this trial will unlikely experience an increase in risk as both groups receive injections. This study is designed to minimally change patient's care. Subjects participating in this trial are chosen due to the clinic consultation scheduled. No change in patient care will happen if the subject is consented. All subjects will be asked to return for three follow-up visits for observation and surveys.

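### The plan calls itself a comparison of fillers and reports by arm, but it defines no arms or allocation, so any contrast between products would probably be confounded by the reasons for choosing each product

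*Combined protocol and SAP*

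**What the plan says.** **Wording that implies a comparison.** The Methodology row of the Study Summary reads "Prospective comparison of the dermal fillers for the treatment of age related aesthetic changes". The two primary objectives in Section 2.1 are "To determine and compare patient reported outcomes and satisfaction with the validated survey FACE-Q over 90 days" and "To determine and compare the volumetric changes over 90 days". Section 8.4.1 summarises "study outcome measures at each visit, both overall, and within each arm". Section 8.4.2 states "The validated FACE-Q will be used to determine patient satisfaction for each arm", then adds regression and analysis of variance without naming a factor or covariate.

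**Treatment actually described.** Section 3.1 gives Restylane-L or Lyft, plus Silk. Section 5.2.1 describes one study group treated in the nasolabial folds, marionette lines and lips as the investigator recommends. The Study Summary gives the reference therapy as None. Section 5 has "Restylane-L® Lyft used for severe nasolabial folds and or marionette lines up to a total of 2 cc (1 cc/side"), while Restylane-L in the same areas carries no severity condition and a 4 cc maximum. Silk is the only filler that Section 5 lists for the lips.

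**Wording that fits neither picture.** Section 8.5 defines the analysis population as randomised patients who kept to their assigned treatment, and Section 9.7 mentions the last patient randomised. Section 11.2 says "If assigned to the control group, they may not receive the desired benefits of the requested consultation". Section 11.3 says "Subjects participating in this trial will unlikely experience an increase in risk as both groups receive injections".

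**The concern.** An analyst told to report by arm, in a study described as comparing fillers, has to build arms from something. The obvious candidate is the product received. Nothing in the described conduct makes those groups comparable: the investigator chooses, and the one product rule stated for the folds in Section 5 is severity. A difference in FACE-Q or volume between Restylane-L and Lyft patients could then reflect who had deep folds, and be published as a difference between products. The manufacturer supplies all three products, so such a claim would be read closely.

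**Working it through.** **Step 1: is there an allocation mechanism?** Sections 8.5 and 9.7 use the word randomised, and Section 11.2 speaks of assignment. No section gives a method, a ratio, strata or a control treatment. Section 5.2.1 has one group and the reference therapy is None. The described conduct is a single cohort with treatment chosen by the investigator.

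**Step 2: what separates the products?**

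| Contrast | What differs besides product | Source |
|---|---|---|
| Restylane-L vs Lyft, folds and lines | Severity and investigator judgement | Sections 5, 5.1, 5.2.1 |
| Same, for volume | Also the stated maximum: 4 cc vs 2 cc | Section 5 |
| Silk vs either | Facial area; no patient is planned to be without lip treatment | Sections 5, 5.2.1 |

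Lyft is also listed for the malar region, so product groups need not be mutually exclusive. Each post-treatment FACE-Q follows the combined treatment. Volume is measured on the treated area (Section 8.4.2), so that last objection applies to FACE-Q and not clearly to volume.

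**Step 3: could analysis repair it?** Table 4 and Section 6.1.1 list no fold-severity grade, and Section 8.4.2 names no covariate. Pre-injection FACE-Q and Vectra images (Section 6.1.2) and standard photographs (Section 3.1.2) are taken, so partial adjustment is possible but not prespecified.

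**Step 4: size, as an illustration.** Section 8.3 gives no alpha, effect, SD or split, so there is no power figure in the plan to reproduce. From the documents: N = 100. Assumed: two exclusive groups, no true product effect, two-sided 5% test, outcome in SD units, severity effect g, and difference q in the share of severe cases.

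- Bias: b = g × q.
- Standard error at 50/50: √(1/50 + 1/50) = 0.200. At 70/30: √(1/70 + 1/30) = 0.218.
- Chance of a significant result: Φ(b/SE − 1.96) + Φ(−b/SE − 1.96).
- Example: g = 0.5, q = 0.75 gives b = 0.375. At 50/50, b/SE = 1.875 and Φ(−0.085) ≈ 0.466; the second term is negligible.

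| g (SD) | q = 0.75, 50/50 | q = 1, 50/50 | q = 0.75, 70/30 |
|---|---|---|---|
| 0.2 | 12% | 17% | 11% |
| 0.5 | 47% | 71% | 41% |
| 0.8 | 85% | 98% | 79% |

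The nominal rate is 5%. A non-central t calculation at 50/50 with q = 1 agrees: 32%, 70% and 98% for g = 0.3, 0.5 and 0.8.

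More patients would not help. With 100 per group, SE = √(2/100) = 0.141, b/SE = 2.65, and the 47% becomes Φ(0.69) ≈ 76%. The bias itself stays at 0.375 SD.

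**The case against.** The strongest reply is that no between-filler test is written down. The analysis of variance names no factor and could run across visits. Comparing over 90 days in Section 2.1 can mean over time. The Study Summary's own objectives and the endpoints in Sections 3.1.4 and 8.1 are single-group quantities, and elsewhere comparison means satisfaction against volume (Sections 1.1 and 7.1). On that view, arm is leftover template wording. This stands in part: a reader might infer that following the plan must produce a by-product test, and the documents do not go that far. But the Methodology row names the fillers as what is compared, and arm remains undefined.

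A reader might also infer that product and severity are tied by design. They are not strictly tied. The Study Summary lists Lyft in the folds without a severity condition, Section 1.2 describes both fold products for moderate to severe folds, and Section 5.1 allows Restylane-L in severe folds. Severity is a tendency alongside investigator judgement. Nor is adjustment impossible, given the baseline measurements in Step 3. And severity is the wrong explanation for Silk, where the confounder is facial area.

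Finally, if patients really were randomised, confounding by severity would not follow. Sections 8.5 and 9.7 use that word, but no procedure supports it, and Section 5.2.1 describes something else.

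**Conclusion.** The plan needs correcting. It announces a comparison of fillers and reporting by arm, while describing one cohort treated on the investigator's recommendation. Any Restylane-L versus Lyft contrast is likely to be confounded by severity and judgement, and for volume by the different stated maxima as well. Silk cannot be compared at all except across facial areas. The single-group endpoints, namely within-patient change in FACE-Q and volume and their correlation, do not depend on a product contrast and are untouched.

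The error rates are not estimates for this trial. They rest on assumed severity effects, splits and separation, none of which the documents give, and the highest figures need complete separation by severity. What does not depend on those figures is that the described design supports no ranking of fillers and no effect against control.

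**What to change.** 1. **Study Summary and Section 2.1:** state the objective as within-patient change in FACE-Q and in volume from the pre-injection reading to Days 14, 28 and 90, in one cohort.
2. **Study Summary (Statistical Methodology), Sections 8.4.1 and 8.4.2:** replace reporting by arm with descriptive summaries by product and area. Name visit as the within-patient factor in the analysis of variance. State that no between-product test or claim will be made.
3. **Section 6.1.1 and Table 4:** record a fold-severity grade per area at the Day 1 consultation, before injection, and report it beside the product summaries. Say that product and severity may overlap too little to be separated.
4. **Sections 8.5 and 9.7:** reconcile the randomised and assigned-treatment wording with the one-group design. Do the same for the control-group and two-group sentences in **Sections 11.2 and 11.3**, and check that the consent form does not repeat them.
5. **Section 5, the Study Summary and Sections 1.2 and 5.1:** reconcile the wording on Lyft in the folds. Which clinical wording is right is for the sponsor and investigator.

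The cost is protocol wording plus one consultation item per area. What is given up is a between-filler claim that the described design cannot support. If that claim is wanted, it needs defined arms and a described allocation, which would be a different study.

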1.1 Background and Relevant Literature

Dermal fillers have been approved for the treatment of age related aesthetic changes, including facial volume loss, and attenuation of the static and dynamic rhytid. Despite widespread use of volumizing fillers there is little data quantifying the subjective benefit of these minimally invasive treatments from the patient perspective. Furthermore, there is little data comparing the subjective benefit with true objective volumetric results. Such data will provide much needed information for patient counselling and treatment optimization for patient perceived outcomes.

1.2 Name and Description of the Investigational Product

Three different dermal fillers will be utilized in this study. All products are FDA approved. Restylane-L® has FDA 510(k) approval for the indication for mid-to-deep dermal implantation for moderate to severe facial wrinkles and folds, such as nasolabial folds and marionette lines. Restylane-L® Lyft is FDA approved for the indication of implantation into the deep dermis to superficial subcutis for the correction of moderate to severe facial folds and wrinkles, such as nasolabial folds and marionette lines and malars (cheek/cheek bone area). Restylane Silk has FDA approval for the indication indicated for submucosal implantation for lip augmentation and dermal implantation for correction of perioral rhytids in patients over the age of 21.

2 Study Objectives

The primary object of the study is to evaluate patient reported outcomes following minimally invasive rejuvenation using FDA approved dermal fillers.

2.1 Primary Objective

- To determine and compare patient reported outcomes and satisfaction with the validated survey FACE-Q over 90 days.
- To determine and compare the volumetric changes over 90 days

2.2 Secondary Objectives

- Determine facial volumetric changes after treatment and correlate to patient reported outcomes.

3 Investigational Plan

Screening will be completed during the clinic visit, and then the patient will be approached for informed consent process. Once the patient is consented, the baseline data will be collected. 3-D Vectra imaging will occur before and after the injections at the initial visit and then again at 14 days, 28 days and 90 days post injection with the FACE-Q survey.

CONFIDENTIAL

This material is the property of the University of Pennsylvania.

3.1 General Design

This is a prospective study to evaluate the efficacy and to determine patient reported outcomes of dermal fillers. Screening will be performed during the patient's office visit. Approximately 100 patients will be enrolled. Patients will participate up to 90 days (Day 1, 14 days, 28 days, and 90 days).

Treatment – Restylane-L® or Restylane-L® Lyft, and Restylane Silk®

3.1.1 Screening Phase

Eligible subjects will be identified from all the principal investigators' clinical schedules, as well as recruiting local population including employees. Potential subjects will be screened by a member of the study team for eligibility using the electronic medical record (EMR) according to the inclusion/exclusion criteria. A member of the study team will give a written informed consent and will answer any questions the patients many have. Eligible patients may be contacted at home through a phone call by a member of the study team to introduce the study. A member of the study team will answer any questions the patient may have before and after the informed consent form is signed. The informed consent form will be documented in the subject's medical record or comparable source document.

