3.1.2 Study Intervention Phase

Intervention will occur during the patient's previously scheduled office visit. The patient will be seen by the PI for the originally scheduled consultation. After the initial consultation, proper screening, and informed consent of the patient is completed the patient will answer one survey and undergo 3-D photography and standard digital photography. After injections the patient will have photographs and the survey administered again before the initial visit is complete.

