4.3 Subject Recruitment

Eligible subjects will be identified from principal investigator's clinic schedule and recruited from local area including employees. Potential subjects will be screened by a member of the study team for eligibility, using the electronic medical record (EMR), according to the inclusion and exclusion criteria listed above. In clinic, the principal investigator will introduce the study to eligible patients. A member of the study team will give a written informed consent, and will answer any questions the patients may have. Eligible patients may be contacted at home through a phone call by a member of the study team to introduce the study to assess interest in participation. A member of the study team will answer any questions the patients may have before and after the informed consent is signed. The informed consent process will be documented in the subject's medical record or comparable source document.

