5.2 Intervention Regimen

5.2.1 Study Group

The patient will receive the injections of the fillers in all three areas the nasolabial folds, marionette lines, and lips as recommended by the PI during the initial consultation of the regularly scheduled appointment.

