10.1 Study Monitoring Plan

This study will be closely monitored by the PI and the project manager. The PI will be participating and the data will be collected by the PI and one other study team member from the patient's EMR. The study team member will enter the data into the REDCap and the project manager will monitor the entry to verify the compliance with respect to the protocol, data collection and source documents.

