11.4 Informed Consent Process / HIPAA Authorization

Eligible subjects will be identified from the practice of the PI. Potential subjects will be screened by a member of the study team for eligibility, using the electronic medical record (EMR), according to the inclusion and exclusion criteria listed above. In clinic, the participating investigator will introduce the study to eligible patients during the consultation visit. A member of the study team, identified to consent, will give a written informed consent and answer any questions the patients may have. Eligible patients may be contacted at home through a phone call by a member of the study team to introduce the study followed by presenting the consent form during the consultation visit. A member of the study team will answer any questions the patients may have before and after the informed consent is signed. It will be emphasized to the potential subject that three visits are required which are not considered standard of care. The informed consent process will be documented in the subject's medical record or comparable source document.

12 Study Finances

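### The protocol describes its source population in two incompatible ways, and sets no rule for excluding, recording or analysing employees who enter a self-reported satisfaction study

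*Combined protocol and SAP*

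**What the plan says.** Two sections define recruitment widely. Section 3.1.1 (Screening Phase) takes subjects from the investigators' clinic schedules, "as well as recruiting local population including employees". Section 4.3 (Subject Recruitment) says subjects are taken from the clinic schedule and "recruited from local area including employees". Neither limits the number or share of employees.

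Four sections describe a narrower group:

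- 3.1.2: "Intervention will occur during the patient's previously scheduled office visit".
- 5.2.1: treatment is given "as recommended by the PI during the initial consultation of the regularly scheduled appointment".
- 11.3: "Subjects participating in this trial are chosen due to the clinic consultation scheduled".
- 11.4: "Eligible subjects will be identified from the practice of the PI".

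Section 6.1.1 leans the same way, since initial screening uses the medical record of the most recent office visit. Section 11.3 adds that consenting brings no change in care.

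Section 4.1 restricts entry by sex and age. Section 4.2 lists surgical, medical and pregnancy exclusions and says nothing about employment. Section 6.1.1 lists the baseline variables taken from the record, and recruitment source is not among them. FACE-Q satisfaction is part of the primary endpoint (3.1.4, 8.1) and enters the secondary correlation (3.1.5, 8.2). On data handling, section 10.1 says "the data will be collected by the PI and one other study team member", with the project manager checking entry.

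**The concern.** The two descriptions lead to different studies. A woman who already had a consultation booked would have been seen without the study. A woman recruited from the staff or the neighbourhood may be treated because of it, with product supplied by the manufacturer (5.3, 12.1). The no-change-in-care statement in 11.3 fits the first woman and not clearly the second.

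The statistical stake is the FACE-Q result. As written, the recruitment rule admits a member of the study team or someone who reports to the investigator. Such a person may find it harder to decline, to report disappointment or to leave. The investigator is one of the two people collecting the data, and section 9.7 keeps names and birth dates in the study database. The treatment sections describe one study group (5.2.1) and the Study Summary gives no reference therapy, so no comparison would cancel a favourable tendency. With no planned source field, the analysis has no specified means of showing whether it occurred.

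**Working it through.** **The plan's own figure.** Total accrual is 100 (4.5). Section 8.3 gives no alpha, power, effect size, SD or dropout, so 100 cannot be reproduced. The point does not depend on how it was derived.

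**Comparing the sections.**

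1. Sections 3.1.1 and 4.3 name two sources: the clinic schedule, and local people including employees.
2. Sections 11.3 and 11.4 name one source: the practice, with selection because a consultation was scheduled. Sections 3.1.2 and 5.2.1 place treatment at that scheduled visit.
3. A local recruit could book a consultation before enrolling, which would satisfy 3.1.2 and 5.2.1. It would not satisfy 11.3, because she would be booking on account of the study, whereas 11.3 makes the existing booking the reason for selection.
4. So 11.3 and 11.4 cannot both be right alongside 3.1.1 and 4.3.

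**Illustration of size.** All shares and shifts here are assumptions; the documents give neither. Let f be the employee share and d the amount, in SD units, by which employees score higher.

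- Bias in the overall mean = f × d. Low: 0.10 × 0.3 = 0.03 SD. High: 0.30 × 0.8 = 0.24 SD.
- Standard error of a mean = 1/√100 = 0.10 SD, so the bias is 0.3 to 2.4 standard errors.
- 95% half-width = 1.96 × 0.10 = 0.196 SD. The bias exceeds this only if d > 0.196/0.30 = 0.65 at f = 30%, or f > 0.196/0.8 = 24.5% at d = 0.8.
- Coverage of a nominal 95% interval when the bias is b standard errors = Φ(1.96 − b) − Φ(−1.96 − b). For b = 1 this is about 83%. For f = 25% and d = 0.5, the bias is 0.125 SD, b = 1.25, and coverage is about 76%.

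**What a recorded source could show.** With 100 subjects, the standard error of an employee versus non-employee difference is √(1/n₁ + 1/n₂) in SD units. For a true difference of 0.5 SD, two-sided 5% power is about 32% at a 10% employee share (90 v 10), 58% at 25% (75 v 25) and 71% at 50% (50 v 50). The sensitivity result should therefore be read as estimates side by side, and a non-significant difference would not rule bias out.

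**The case against.** The strongest reply is that this is a wording conflict and the bias is conjecture. Much of that is fair.

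- **The size is assumed.** Both f and d are invented, and the range spans a factor of eight, from negligible to material. This stands.
- **A constant offset cancels in change scores.** FACE-Q is also given before injection (6.1.2). If employees score higher by the same amount throughout, change from baseline is unaffected and only a differential arising after treatment remains. This stands, although section 8.4.2 does not say that change scores will be analysed.
- **Volume is measured by software** (8.4.2), so that half of the primary endpoint is not directly affected. This stands.
- **Section 11 may hold leftover text.** Sections 11.2 and 11.3 mention a control group and two groups that the treatment sections lack. That may explain the conflict but does not remove it, since 3.1.2 and 5.2.1 also describe scheduled patients.
- **General protections exist:** withdrawal at any time without effect on care (6.4) and IRB-approved consent (section 11). Neither addresses employees.

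A reader might also infer more than the text supports:

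- That staff would be rating their own institution's injector. The endpoint is satisfaction with the correction, no FACE-Q scale on the injector is named, and the employer is not stated; the health system is only the likely reading, as the single site.
- That the investigator alone selects, injects and collects. Study-team members screen, no section says who injects, and two people collect the data.
- That employees could not be identified afterwards. The documents support only that no field is specified; the baseline CRF is not included.
- That recruitment has no limits. Age, sex, the exclusions and the total of 100 all apply; only the employee share is uncapped.

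**Conclusion.** The conflict between sections 3.1.1 and 4.3 on one side and 3.1.2, 5.2.1, 11.3 and 11.4 on the other is real and needs to be reconciled. It would go too far to say that the trial enrols a population other than the one described, because section 4.3, the recruitment section, describes the wider source openly. What the documents support is that the source population is described in two incompatible ways and that nothing governs the exclusion, recording or analysis of employees.

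A favourable-response tendency in FACE-Q and in its correlation with volume is plausible, and following the recruitment rule as written would admit the people in whom it is most likely. Its size is not derivable. The range of 0.03 to 0.24 SD rests wholly on an assumed share of 10% to 30% and an assumed shift of 0.3 to 0.8 SD, and for change scores it applies only to the part of the shift that arises after treatment. The matter should be corrected because the changes are cheap and source is easiest to record at enrolment. The documents do not show that the satisfaction result would be invalid.

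**What to change.** 1. Add to section 4.2 an exclusion for study-team members and staff who report to the investigator.
2. Record recruitment source at baseline in three categories: scheduled clinic patient, employee, other local volunteer.
3. In section 8.4.2, plan a sensitivity analysis in scheduled clinic patients alone, set beside the full set. It should cover the FACE-Q results, including change from the pre-injection score, and the FACE-Q–volume correlation.
4. Reconcile sections 3.1.2, 5.2.1, 6.1.1, 11.3 and 11.4 with the recruitment allowed in 3.1.1 and 4.3, including the no-change-in-care statement in 11.3.

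The cost is amendment wording, one CRF field, one extra table and a few potential recruits. The exclusion does not deal with bias from other employees, who would remain eligible; the sensitivity analysis is meant to show that part. It will be less precise than the full-set result: if, for example, 25 of 100 women were not scheduled clinic patients, the 95% half-width would widen from 0.196 SD to 1.96/√75 = 0.226 SD.
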